Urine: Urine is collected in a sterile leak proof container. If the patient has a foley catheter, the injection port at junction of drainage tubing is cleaned with betadine. Needle is inserted and urine aspirated into the syringe. Urine is then transferred into the urine container. If a urine collection bag is used, the urinary meatus is cleansed and the urine bag is applied to collect the urine.

Urine specimen is sealed and transported to the laboratory as soon as possible, no longer than 1 hr. Samples are inoculated on BAP and EMB plates with a calibrated loop and incubated for 24 hours.

A separate plate is routinely used to assess for fungus. Please note that regarding fungal cultures, many of the opportunistic fungi (Aspergillus, Penicillium and Mucor) are rapid growers and colonies will be seen within the first 24-48 hours (mature within 4-5 days) and identified down to the species level when possible. Candida will usually grow in 24-48 hours and can be identified at this time. Speciation requires 72 hours. .

The pathogenic fungi (Histoplasma and Blastomyces) cultures will be referred to the MGH laboratory for speciation. Results are confidentially reported to the medical team at Shriners Burns Hospital.

Contaminates may be found among urine cultures. The decision on whether or not it is a contaminant is based on the clinical judgment of the medical doctors and clinical team. . If a culture is deemed a “contaminant” it will be reported as such in the data collection sheet.

Sputum: Sputum and aspirates are collected in a sterile cup or suction trap. Non-bacteriostatic normal saline may be instilled into the airway to aid in procurement of culture. Specimen container is placed in a plastic bag, sealed and brought to the laboratory as soon as possible. Sputum is plated onto 3 different agar plates: TSA with 5%sheep blood, Levine EMB and Chocolate plates. Plates are incubated in a CO₂ incubator for 24 hours and if no organisms are seen (or scant growth) they are reincubated for another 24 hours.

A separate plate is routinely used to assess for fungus. Please note that regarding fungal cultures, many of the opportunistic fungi (Aspergillus, Penicillium and Mucor) are rapid growers and colonies will be seen within the first 24-48 hours (mature within 4-5 days) and identified down to the species level when possible. Candida will usually grow in 24-48 hours and can be identified at this time. Speciation requires 72 hours. .

The pathogenic fungi (Histoplasma and Blastomyces) cultures will be referred to the MGH laboratory for speciation. Results are confidentially reported to the medical team at Shriners Burns Hospital.

Normal flora cultured from the sputum (viridians strep Neisseria species, coagulase negative Staphylococcus and rare amounts of yeast, enteric gram negatives, Staph. aureus.) will be documented as normal flora)

Dietary Data

Dietary data (enteral nutrition, parenteral nutrition, oral intake) will be collected daily from the medical record. Total Se intake via supplements and/or enteral feedings will be calculated based on daily intake and output sheets as recorded by the bedside nurse. Dietary Se intake from food will be determined using the Nutrient Database System for Research version 2005.

Other Data

Weights will be obtained as part of routine care by the bedside nurse, and recorded twice a week. Demographic data will be obtained from the medical record. Please see data collection sheet for details.

As part of routine care by the medical team neurological status will be assessed and several laboratory values will be monitored closely (including total protein, albumin, prealbumin and C-reactive protein complete blood count, serum creatinine, AST, ALT, alkaline phosphatase, total bilirubin, and coagulation studies) will be recorded from the medical record.

D. Selenium Analysis

Blood (4 ml or 8 ml) and urine samples will be obtained weekly. De-identified samples will be sent to a commercial laboratory for analyses. Results will be sent to Shriners Burns Hospital in Boston. Additionally, to ensure the safety of all patients, once every 2 weeks, blood samples (4 ml) will also be sent to the Massachusetts General Hospital Chemistry lab for analysis. These results are typically available after 24-48 hours.

The study endpoint will be whichever of the following factors happens first:

- 8 weeks
- discontinuation of central venous catheter
- a stop in Se/Placebo infusion lasting longer than 48 consecutive hours or 72 hours in 1 week,
- when the patient achieves 95% definitive wound closure determined by the attending physician.

No interim analyses are planned. Data obtained from our previous investigation on Se and pediatric burns was used for the power analysis calculation:

$$n = (2 \times [Z_{(1-\alpha/2)} + Z_{(1-\beta)}]^2) / \Delta^2$$

where $Z_{(1-\alpha/2)}$ and $Z_{(1-\beta)}$ represent percentage points of the normal distribution for statistical significance level and power, respectively. The values used were 1.96 for a significance level of 5% and 0.8416 for a power of 80%. The Δ represents the standardized difference (the treatment difference divided by its standard deviation). This was calculated by subtracting the mean plasma Se determined in our pilot study (1.08 $\mu\text{mol/L}$) from the average plasma Se of healthy American children 1.35 ($\mu\text{mol/L}$) and dividing by the standard deviation (0.34). This calculation revealed that 25 subjects are needed per group to obtain 80% power and a significance level of 5%.

All subjects enrolled will be included in the statistical analyses (intent-to treat). A 2-sided statistical test will be used for all analyses and the overall type-I error rate will be controlled at the 5% level. For each dependent variable (plasma selenium, urinary selenium, plasma GPx activity) a 2-way repeated measures ANOVA will be used to examine the difference among groups and over time (primary hypothesis). Tukey's will be utilized as the post-hoc test.

An ordinal logistic regression will be performed to determine the relationship between the incidence of infection (categorized by burn, bloodstream, urinary tract infection, and PNA) and plasma selenium, urinary selenium, plasma GPX, age, initial percent TBSA burned, and treatment group (secondary hypothesis).

Appropriate confounding factors (including but not limited to dietary Se intake, age, sex, race, initial %TBSA, and length of time from burn injury to study enrollment) will be included in the statistical models. All statistics will be completed using SAS software.

VI. Risks and Discomforts

Phlebotomy will be minimal (4 or 8 ml/wk) and will be obtained painlessly through existing catheters or during operative procedures.

Se toxicity is rare. Symptoms include:

- memory loss
- gastrointestinal upset,
- hair loss,
- weakened nails,
- white blotchy nails,
- garlic breath odor,
- metallic taste,
- vomiting,

- sweat
- dermatitis,
- dental defects,
- nervousness,
- mental depression,
- fatigue,
- irritability,
- mild nerve damage,
- Peripheral vascular collapse,
- Internal vascular congestion,
- Hemorrhage,
- Congested and edematus lungs,
- Brick-red color gastric mucosa
- Coma
- Death

Some symptoms of Se toxicity are not specific to Se toxicity and would be difficult to monitor in a pediatric burn patient. Additionally, blood and urine Se values will not be immediately available (being sent to an outside facility for analyses). To assess for toxicity, hair and nails will be monitored weekly for loss, change of appearance, and brittleness. Additionally, to ensure the safety of all patients, once every 2 weeks, blood samples will also be sent to the Massachusetts General Hospital Chemistry lab for analysis of selenium levels. If the selenium level is greater than 100 ug/dL the patient will be immediately removed from the study.

It is important to note that the IOM (31) state in their report that the UL does not apply to patients under medical supervision and that doses of Se above the UL should not be discouraged in clinical trials. Se toxicity has not been reported in trials administering Se supplements to adults with doses up to 1500 ug per day (approximately 25 times the RDA) for short periods of time (1-3 weeks).

VII. Potential Benefits

This study will provide enhanced understanding of Se requirements during burn injury.

VIII. Monitoring and Quality Assurance

All subjects will be monitored for any treatment-related adverse events for 2 weeks following discontinuation of the study therapy. Ongoing adverse events thought to be study drug related will be followed until resolution or the condition stabilizes. Any adverse events will be reported to the Partners Human Research Committee per the guidelines.

Per FDA reporting requirements, serious and unexpected adverse experiences, as well as, unexpected fatal and life-threatening experiences related to this study will be reported to the FDA no later than 7 days after the initial receipt of the information. A complete written report of the unexpected fatal or life-threatening experience will be provided to the FDA within 15 calendar days.

According to the FDA, all “Expected” and “Unexpected” adverse events related to this study will be: (1) classified by relation to study treatment, severity, action taken in response to the adverse event, and clinical outcome; (2) collected and recorded in patient case report forms and adverse event datasets; and (3) reported to the Food and Drug Administration (FDA)

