Berger et al. 2006 (34)	Combination of 2 randomised, double-blind trial	41 burn patients with mean TBSA of 46%	IV trace element cocktail vs Placebo. Cu: 2.5-3.1 mg/d Se: 315-380 ug/d Zn: 26.2-31.4 mg/d	8-21 days	Plasma Se levels increased with supplementation; Reduced number of infections in supplemented pts (3.5 vs 2 episodes per pt)
Berger et al. 2007 (53)	Prospective, randomized, placebo-controlled trial	21 burn patients with mean TBSA of 45%	IV trace element cocktail vs Placebo. Cu: 3.75 mg/d Se: 375 ug/d Zn: 37.5 mg/d	14-21 days	Plasma Se sig higher in supplement group; Number of infect in first 30 days was sig lower in supplement group (2 vs 4 infections per

					pt); Supplement group had fewer regrafting episodes.
Berger et al. 1998 (36)	Prospective, randomized, placebo-controlled trial	20 burn patients with mean TBSA of 48%	IV trace element cocktail vs Placebo. Cu: 3.75 mg/d Se: 375 ug/d Zn: 37.5 mg/d	8 days	The number of infections were lower in supplement group

Overall the data among adults is promising, but does not identify a specific guideline for selenium supplementation during critical illness. The data among children is scarce and less impressive.

C. Rationale behind proposed research/ benefits to society

The Se status of children with major burns is suboptimal which may increase the incidence of infection. Se requirements during critical illness are not known. Results from this investigation may provide a tool for recommending Se supplements during burn injury.

II. Specific Aims

The hypothesis of this research is that Se supplementation will restore the depressed Se status among children with burn injuries. The secondary hypothesis is that Se status is related to the incidence of infection among pediatric patients with burns.

The specific aims of this research are

1. to determine the impact of supplemental Se needed on plasma Se, Gpx activity, and urine selenium among pediatric patients with burns $\geq 20\%$ TBSA.
2. to determine the association between Se supplementation, biomarkers of Se status and indicators of stress and infection.

III. Subject Selection

All subjects (n = 75) will be recruited from the Shriners Hospital for Children in Boston.

Inclusion Criteria:

- Between 1 and 18 years of age admitted to Shriners Burns Hospital
- TBSA burn of $\geq 20\%$
- Existing catheter
- Enrolled into study within 3 weeks of burn injury

Exclusion Criteria:

- < 1 year or > 18 years of age
- $< 20\%$ TBSA burn

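### The primary hypothesis is that selenium status will be restored, but no planned analysis compares a dose arm with the healthy plasma average, so a significant result would show only that selenium was raised

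*Combined protocol and SAP*

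**What the plan says.** Section II (Specific Aims) gives the hypothesis as "Se supplementation will restore the depressed Se status among children with burn injuries". Aim 1 in the same section is more modest: it asks what impact supplementation has on plasma selenium, GPx activity and urine selenium.

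The statistical text at the end of section V.D (Selenium Analysis) says that, for each of these three variables, "a 2-way repeated measures ANOVA will be used to examine the difference among groups and over time (primary hypothesis". It adds that "Tukey's will be utilized as the post-hoc test" and that "A 2-sided statistical test will be used for all analyses". The only other planned analysis is an ordinal logistic regression for infection.

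The healthy plasma value of 1.35 µmol/L is used in two places. In the pilot results (section I.B) it shows the deficit: 82% of weekly samples lay below it. In the power calculation (section V.D) it sets the effect size, obtained by "subtracting the mean plasma Se determined in our pilot study (1.08" µmol/L) "from the average plasma Se of healthy American children 1.35" and "dividing by the standard deviation (0.34"). It does not appear in any planned analysis. The documents give no criterion, margin or time point for calling a child or an arm restored.

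**The concern.** Group effects, time effects, their interaction and the Tukey contrasts all compare arms or weeks with one another. None of them compares an arm with a normal value. Because the ANOVA is tied to the primary hypothesis, and that hypothesis speaks of restoration, a significant group difference would naturally be read as support for restoration. It would support only the weaker statement that selenium was raised.

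The distinction matters for how the result will be used. Section I.C says the results may help in recommending supplements during burn injury, and the trial has two dose arms. A test of no difference from placebo cannot separate partial correction, full correction and overshoot.

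**Working it through.** **Inputs, all from sections IV.B and V.D:** 25 children per arm in three arms; placebo mean taken as the pilot mean, 1.08; healthy average 1.35; SD 0.34 (all µmol/L); two-sided 5% level. For the error rates: "The values used were 1.96 for a significance level of 5% and 0.8416 for a power of 80"%.

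**The plan's own figure.** Gap = 1.35 − 1.08 = 0.27. Standardised difference = 0.27/0.34 = 0.794. n = 2 × (1.96 + 0.8416)² / 0.794² = 24.9, rounded up to 25 per group. The stated figure reproduces.

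**Smallest significant difference with the planned Tukey test, one measurement per child.**
- SE of a difference between two arms = 0.34 × √(2/25) = 0.0962.
- Tukey critical value, 3 groups and 72 df, on the scale of a difference divided by its SE: 2.393.
- Smallest significant difference = 2.393 × 0.0962 = 0.230.
- Observed arm mean at that point = 1.08 + 0.230 = 1.31, which is 0.230/0.27 = 85% of the gap.

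**Chance that a partly corrected arm is significant.** Noncentral t with 72 df, noncentrality (true mean − 1.08)/0.0962, Tukey critical value:

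| True arm mean | Share of the gap closed | Significant against placebo |
|---|---|---|
| 1.25 | 63% | 27% |
| 1.30 | 81% | 46% |
| 1.35 | 100% | 66% |

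**Repeated measures.** The documents give no within-child correlation. If k weekly values are averaged with correlation ρ, the threshold difference is multiplied by √((1 + (k − 1)ρ)/k). Over an assumed range of k = 4 to 8 and ρ = 0.3 to 0.7:
- Lowest threshold (k = 8, ρ = 0.3): factor 0.62, so 1.08 + 0.14 = 1.22.
- Highest threshold (k = 4, ρ = 0.7): factor 0.88, so 1.08 + 0.20 = 1.28.

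On these assumptions significance is reached further below 1.35 than with a single measurement.

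**What 25 children can say about restoration.**
- SE of one arm mean = 0.34/√25 = 0.068.
- 95% half-width = 2.064 × 0.068 = 0.14 (t, 24 df).
- Suppose the true mean is exactly 1.35 and restoration requires the lower 95% limit to exceed 1.35 minus a margin. The documents set no margin, so these are illustrations:
  - margin 0.14 (lower limit above 1.21): met about 51% of the time;
  - margin 0.20 (lower limit above 1.15): met about 80% of the time.

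**The case against.** The strongest reply is that the trial answers its main question. Aim 1 concerns impact, and a randomised, double-blind comparison of two doses with placebo measures impact. The same model yields arm means by week, which anyone can set beside 1.35, as the team did with its pilot data. No reporting rule in the documents equates significance with restoration. All of this stands. A reader might infer that the trial cannot answer its question at all, or that it tests nothing but arm differences. The documents support neither: Aim 1 is answered, and change over time is also tested. What is missing is a planned comparison with the healthy value and agreed wording for the conclusion.

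A reader might also take 1.35 as a target or a lower limit of normal. The protocol describes it only as a healthy average. On a normal model about half of a fully restored arm would lie below it, so a large share of children below 1.35 does not by itself show failure.

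Nor does an observed mean below 1.35 prove non-restoration. The Tukey threshold of 1.31 is only 0.04 below 1.35, less than one SE of an arm mean. The chance of a Tukey-significant result with an observed mean below 1.35 is about 21% when the true mean is 1.25 and about 22% when it is 1.35. The pattern cannot tell the two cases apart, and for that reason an interval is needed.

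Finally, section I.A says selenium status should be judged on plasma selenium, GPx and urine selenium together, so looking at plasma alone is partial. That is fair. However, 1.35 is the only healthy value used in sizing the trial, and the other two benchmarks are harder to use. The pilot GPx mean of 3.29 falls inside the quoted 2.8–3.4 range, although 40% of samples were below that range and the printed units differ. Pilot urine selenium (65.9 µg/L) was already above the healthy value (28.7 µg/L).

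**Conclusion.** The point holds in a limited form. The placebo comparison is valid and answers Aim 1. The hypothesis of restoration is not addressed by the analysis assigned to it, and sizing the trial on the full gap of 0.27 does not change this, because rejecting a difference of zero does not show a difference of 0.27. On one measurement with the planned Tukey test, significance begins at an observed mean of about 1.31 (85% of the gap), and an arm that truly closes 63% of the gap is significant in about 27% of trials.

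These figures take the pilot mean as the placebo mean and the pilot SD as common to all arms, as the protocol does, with 25 analysed per arm and normal data. The remedy should be adopted, but it is a matter of analysis and wording and does not call the design into question.

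**What to change.** In the statistical text of section V.D, add for plasma selenium: each dose arm's model-adjusted mean minus 1.35 µmol/L, with a 95% CI, at a time point or average named in advance. State that significance against placebo supports 'raised', and that 'restored' is judged from this interval. Because the interval has two sides, it also shows overshoot. The alternative is to reword the hypothesis in section II to raising selenium status relative to placebo.

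If a formal restoration margin is wanted, the sponsor should set and justify it before unblinding, in the light of the pass rates of about 51% (margin 0.14) and 80% (margin 0.20) for a truly restored arm of 25. The share of children at or above 1.35 can be tabulated by arm, but as description only.

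The cost is a few lines of text and one more estimate per dose arm from data already collected. The downside is that a restoration claim becomes harder to make.

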subjects/parents/ guardians at the bedside, who meet the inclusion/exclusion criteria, with a brief explanation of the study. A more detailed explanation will be offered in a private room to those interested in participation. The alternative to participation is “not to participate”. Care will not be altered for patients who do not participate. Informed consent will be obtained if the patient and/or parent/legal guardian agrees to participate. Parents/legal guardians will be allowed an indefinite amount of time for questions and participation consideration. Parents/legal guardian will provide consent for 0-18 year old children (documented in writing using the PHRC approved consent form). The permission of both parents is required unless one parent is deceased, unknown, incompetent, or not reasonably available or if only one parent has legal responsibility for the care and custody of the child. Any child 14 years or older, who is able, will consent along with parent/guardian. The assent of each child (age 7 and older) who is capable of providing assent based on medical condition, age, maturity, and psychological state will be sought. According to a power analysis calculation, 75 children will be included in this study.

B. Treatment Assignment and Randomization

This is a randomized, double-blind, placebo-controlled trial. Patients will be randomly assigned to receive Selenium supplementation (either 2, or 4 ug/kg/day) or a placebo. 25 subjects will be in each group (total of 75 subjects). Randomization will occur by using a computerized randomization list. A pharmacist, who is not a member of the study staff, will prepare the supplements and label them accordingly prior to distribution.

V. Study Procedures

A. Study Parameters

- B. Lab studies conducted solely for the purpose of this study include plasma and urinary Se, plasma Gpx and dietary Se intake. Other parameters that will be included are demographics, medications, wound debridement procedures, invasive devices, mode of nutrition support, kilocalorie and protein intake, weekly weights, neurological status (as routinely assessed by the clinical team) and routine laboratory studies.

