All patients will receive routine nutrition support that includes oral, enteral, or parenteral nutrition or a combination of the 3 sources. All enteral nutrition products contain Se in the form of sodium selenate (Table 2). All patients who require parenteral nutrition receive 20 ug of IV selenious acid per day (this is standard therapy at SBH). According to our previous study, despite various routes of nutrition support within and among subjects, Se intake remained stable throughout the 8 week time period and cover approximately 150 – 200% of the RDA for Se. Therefore standard nutrition support, including Se, should not interfere with this proposed investigation (Figure 1).

In addition to standard nutrition support, all patients will be randomized to receive IV Se supplementation or placebo. The placebo (0.9% sodium chloride or 5% Dextrose solution, depending on the clinical situation) will look identical to the Se supplements. Patients in the experimental groups will receive parenteral Se as selenous acid (added to 25 ml of 5% Dextrose solution or 0.9% sodium chloride) (carrier solution will depend on clinical situation) as a 24-hour continuous infusion in doses 2 ug/kg/day (n = 25), or 4 ug/kg/day (n = 25). The placebo group (n = 25) will receive sodium chloride 0.9% in the same regimen. These Se supplement amounts were determined taking into account previous studies in the literature, current RDAs, UTLs, ASPEN guidelines for parenteral Se, and dietary data recorded from our previous study. According to reference weights adapted from NHANES III data, supplement doses (2 ug/kg/day and 4 ug/kg/day) do not exceed the upper tolerable limits for children.

The Se/Placebo will be provided as a 24-hour continuous infusion. The continuous infusion of Se/Placebo may be temporarily interrupted, if necessary, for reasons including, but not limited to, surgical procedures and drug compatibility issues. These temporary interruptions will not reduce the integrity of

the study. However, if the Se/Placebo infusion is held for longer than 48 consecutive hours or 72 hours in 7 days then the subject will be removed from the study. At this time no further study drug will be given or biological samples taken. All subjects will be monitored for any treatment-related adverse events for 2 weeks following discontinuation of the study therapy.

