Prior to initiation of the study, the research nurse will hold an in-service for clinical staff to alert them of the study. A specific research sticker will be placed in the chart to alert clinical staff that the patient is enrolled in this research study. The MD responsible for the care of the patient will write the orders for the supplements. The Pharmacy will prepare all supplements and the nurses will administer them.

C. Data Collection

Plasma and urine Se and plasma Gpx will be measured weekly from the time of admission for a maximum of 8 weeks or until the patient achieves 95% definitive wound closure.

The research nurse will obtain 4 ml or 8ml (8 ml will be drawn instead of 4 ml every other week starting with week 1 for real time analysis) of whole blood off an existing catheter and place it into a trace-element free blood collection tube.

Every other week, when 8 ml of blood is needed, 4 ml will be transferred by the unit assistant to the MGH laboratory for immediate analyses (the MGH lab uses Quest Labs for analysis of selenium). If in the unlikely event that the MGH lab rejects the sample for any reason, another 4 mL blood draw will be collected and sent to the MGH lab for real-time analyses.

Weekly, the 4 ml sample will be transported by the nurse to the clinical research lab (in the same building). In the lab the nurse will use a centrifuge to separate the blood and then pipette the plasma and whole blood into collection vials to be frozen prior to analyses. A 24 hour urine will be initiated the day prior to blood sampling for analysis of urinary Se. Urine will be collected via an existing catheter. If no catheter exists patient will be asked to urinate into a container. If the patient is unable to urinate into a container, the urine sample will not be collected. Infant urine will be collected via diapers. The research nurse will then bring the urine container down to the clinical research lab and aliquot it into 50 ml vials prior to being frozen. Frozen samples are eventually mailed to a commercial laboratory for lab analyses. The PI is certified to ship biological products and all appropriate regulations will be followed.

Culture Data

Wound cultures will be obtained for all patients admitted to the acute care unit at Shriners Burns Hospital, per routine care, on admission. Urine cultures will also be obtained upon admission if one or more of the following criteria are met:

- Symptoms of urinary tract infection (UTI)

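### The placebo is described as saline or dextrose and then as saline only; if the second rule is followed and staff can learn the carrier, a dextrose infusion reveals active treatment

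*Combined protocol and SAP*

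**What the plan says.** Three statements stand close together in one paragraph of section V.B (Supplements to be used):

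1. On the placebo product: "The placebo (0.9% sodium chloride or 5% Dextrose solution, depending on the clinical situation) will look identical to the Se supplements".
2. On the two active doses: selenous acid is added to 25 ml of either dextrose or saline, and the "carrier solution will depend on clinical situation".
3. On the placebo arm's regimen: "The placebo group (n = 25) will receive sodium chloride 0.9% in the same regimen".

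Section IV.B (Treatment Assignment and Randomization) declares the design: "This is a randomized, double-blind, placebo-controlled trial". It allocates 25 children to each of three groups. On preparation it says: "A pharmacist, who is not a member of the study staff, will prepare the supplements and label them accordingly prior to distribution". It does not say what the label shows.

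Section V.B also covers ordering: "The MD responsible for the care of the patient will write the orders for the supplements". Nurses give the infusions.

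**The concern.** Statements 1 and 3 cannot both govern. Under statement 1 the placebo has the same two carrier options as the active infusions. Under statement 3 it has one, so dextrose can occur only in the active arms. Statement 3 sits with the regimens of the individual arms, and a pharmacist could reasonably take it as the working instruction.

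What is at stake is the blind among staff whose decisions feed the data:

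- **Infection criteria (section V.A, Study Parameters).** Some urinary tract criteria are met by a physician's diagnosis or by starting treatment. Some bloodstream criteria depend on the physician starting antimicrobial therapy.
- **Contaminant calls (section V.C, Culture Data).** Whether a blood or urine culture is a contaminant is left to clinical judgement.
- **End of follow-up (sections V.B and V.D).** Infusion holds beyond the stated limits, and the attending physician's finding of 95% wound closure, end a child's participation and sampling.

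Infection is the secondary hypothesis, and treatment group is a term in its regression model.

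**Working it through.** The documents give no figure on carrier use, so there is none to reproduce. The only inputs are the allocation and the two placebo rules.

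**Inputs**

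- Allocation (section IV.B): 25 + 25 + 25 = 75, that is 50 active and 25 placebo. From allocation alone, P(active) = 50/75 = 66.7% and P(placebo) = 25/75 = 33.3%.
- d, the share of active children whose infusion is in dextrose throughout. This is **not in the documents**, so a range is assumed. It is a share of children with a fixed carrier, not of infusions.

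**Matched rule (statement 1, with the carrier chosen independently of arm)**

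- P(active | dextrose) = 50d / (50d + 25d) = 66.7%
- P(placebo | saline) = 25(1 − d) / [25(1 − d) + 50(1 − d)] = 33.3%

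Both equal the allocation probabilities, so the carrier carries no information.

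**Saline-only rule (statement 3)**

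- P(active | dextrose) = 50d / (50d + 0) = 100% for any d above zero
- P(placebo | saline) = 25 / [25 + 50(1 − d)]

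| d (assumed) | Active children on dextrose, 50d | Share of all 75 | P(placebo given saline) |
|---|---|---|---|
| 0% | 0 | 0% | 25/75 = 33.3% |
| 10% | 5 | 6.7% | 25/70 = 35.7% |
| 25% | 12.5 | 16.7% | 25/62.5 = 40% |
| 50% | 25 | 33.3% | 25/50 = 50% |
| 75% | 37.5 | 50% | 25/37.5 = 66.7% |

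The second and third columns count children who could be identified as active by someone who knows the carrier. Dextrose separates active from placebo only; it does not separate 2 from 4 µg/kg/day.

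**The case against.** The best defence is that the saline-only sentence may be a drafting remnant. The sentence that addresses matching gives the placebo both carriers, and if pharmacy works to it and chooses the carrier independently of arm, nothing leaks. That is fair, but no other part of the document says which sentence governs.

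The next objection concerns visibility. A reader might infer that the blind is broken outright because nurses and physicians see the carrier. The documents do not support that. The placebo is to match the active product in appearance, the pharmacist is outside the study staff, and label content is not given. A blinded physician's order cannot vary by arm, so a saline-only placebo would have to be a pharmacy substitution, noticed only if the label or record names the true carrier. This objection stands as a limit: disclosure is an inference. It is plausible, because the carrier depends on the child's situation, the treating physician orders, nurses administer, and nothing says the carrier is concealed. Matching appearance does not hide a solution named in an order or on a label. If a child ordered dextrose visibly received saline, that substitution would itself point to placebo.

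A reader might also infer that any effect of the carrier would be inseparable from treatment. That goes too far. Unless every active child receives dextrose, active and placebo children on saline can be compared, as can dextrose and saline within the active arms. Carrier choice follows the clinical situation, so there is partial confounding and no more. The quantity is also small: 25 ml × 5% = 1.25 g of dextrose a day, and nothing in the documents shows that this would matter.

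Finally, the primary hypothesis concerns plasma selenium, urinary selenium and plasma GPx. These are measured on de-identified samples at a commercial laboratory, and knowing the carrier can hardly bias the assays. Many infection criteria use cultures, histology or radiographs, and the Infection Control Nurse clarifies cases. This stands and narrows the exposure. What remains exposed are the criteria and decisions that rest on the treating team. Wound closure matters because it stops follow-up; it is not an analysed outcome.

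**Conclusion.** The two placebo descriptions conflict and must be reconciled; this is certain from the text. The unblinding is conditional on two things: that the saline-only sentence is followed, and that ordering or bedside staff can learn the carrier. If both hold, a child on dextrose is known to be active, and P(placebo | saline) rises from 33% to between 36% and 67% as d goes from 10% to 75%. At the low end the shift for children on saline is slight.

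These figures assume one fixed carrier per child. Infusions may run for up to 8 weeks and the carrier could change, so d should not be read as a share of infusions; the share of children ever identified could then be higher.

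The exposure falls mainly on the physician-influenced infection criteria and contaminant calls, and on holds and wound-closure decisions, which also determine how many weekly samples a child contributes. The selenium and GPx measurements themselves are little exposed. The point should be corrected, but it does not by itself undermine the primary comparison.

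**What to change.** Reconcile the two placebo sentences in section V.B, and the pharmacy instruction that follows from them, so that one carrier rule applies to all three arms. The text should state that:

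- the carrier is chosen and recorded without reference to allocation; and
- the placebo is supplied in the same carrier the child would have had on active drug.

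Which carrier suits which situation stays with the clinicians; this point takes no position on it.

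Under such a rule the carrier carries no information about arm, as the working shows. Sample size and analysis are unchanged. The cost is a minor protocol amendment with its usual committee review.
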